7.0 Expected Risks/Benefits

- There are potential benefits for participants including improved visual clarity. Contact lens prescription is the current standard of care for keratoconus. There are associated risks associated with contact lens use including eye pain, epithelial defects, microbial keratitis, corneal scarring and neovascularization.
- There are potential risks associated with new contact lens wear including handling issues and loss of contact lens. This may result in eye pain, epithelial defects, microbial keratitis, corneal scarring and neovascularization. These issues are not specific to the study but with wearing/using new contact lens in general.

8.0 Data Collection and Management Procedures

- Paper case report forms will be completed at each site.
- De-identified data only will be entered into the RedCAP database by each investigator.
- De-identified data will be stored in RedCAP for future analysis and publication.

9.0 Data Analysis

- Final lens selection will be calculated for each randomization group.
- Descriptive statistics will be used to compare logMAR visual acuity, comfort (OSDI and CLDEQ) and number of lenses ordered to achieve fitting for lens #1 and lens #2. Meibography will be analyzed.

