3.0 Objectives/Aims

- Specific Aim;
- This study will prospectively compare visual satisfaction and ease of use between corneal gas permeable and scleral lenses for patients with mild to moderate keratoconus who are naïve to lens use.

- Hypotheses to be tested:
 1. Participants will select scleral lens over corneal gas permeable lens as their preferred final lens type. Scleral lens comfort will be rated higher than corneal gas permeable lenses.

- Primary Outcome Measure:
 1. The Primary outcome of this study is participant selected final lens choice for continued use for the management of keratoconus.

- Secondary Outcome Measures:
 1. Best corrected Snellen visual acuity converted to logMAR
 2. Practitioner ease of lens fitting including number of visits, number of trial lens required for fitting and number of lenses ordered.
 3. Patient burden including time required to learn safe application and removal as well as daily time require for lens application and removal.
 4. Subjective comfort with lens use rated on comfort scale of 0 (not comfortable) to 10 (very comfortable)
 5. Dry eye symptoms assessed using the validated OSDI and CLDEQ do we get baseline meibography on each patient.
 6. Impact of lens cost on lens choice.

Methods:

- Patients will be consented and enrolled in the study during routine clinical visits.
- At the first study visit, participants will be fit with corneal gas permeable and scleral lenses in both eyes. The OSDI and CLDEQ questionnaires will be assessed.
- The patient will return for regularly scheduled fitting visits to maximize lens fitting and visual acuity.
- At the 2nd study visit, patients will be randomized to receive lens application and removal training with lens type #1. Patients will begin daily wear of lens type #1.

- At the 3rd study visit (2-4 weeks after dispensing of lens #1), visual acuity, ease of use and subjective comfort of lens #1 will be assessed. The OSDI and CLDEQ questionnaires will be repeated.
- The participant will be trained in lens application and removal with lens #2. Lens #1 will be returned to the study clinician unless the patient refuses (thus ending the study).

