- At the 4th study visit (2-4 weeks after dispensing lens #2), visual acuity, ease of use and subjective comfort of lens #2 will be assessed. The OSDI and CLDEQ questionnaires will be repeated. Participants will be asked to select their final lens of choice. Participants unable to return for a study visit will be contacted to complete the surveys and final lens preference,

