6.0 Study Design and Procedures

- Multi-center study sites will include:
 - .1 Illinois Eye and Ear Infirmary, Chicago IL.(UIC)
 - .2 Millennium Park Eye Center, Chicago, IL. (UIC)
 - .3 The Mayo Clinic, Rochester MN.
 - .4 The Ohio State University, Columbus OH.
 - .5 The Illinois College of Optometry, Chicago IL.

- This is a prospective, multi-center, randomized interventional clinical trial with a 2x2 crossover design of patients with keratoconus fit with corneal and scleral gas permeable contact lenses. The crossover design allows intra-subject differences between two randomized groups with participants serving as their own controls.
- This is a pilot study to determine sample size and feasibility of study protocol for a larger randomized study.
- Each clinic will enroll up to 25 participants with a maximum of 125 participants.

- Screening eligibility
 - .1 Patients age 18 or older with a diagnosis of keratoconus will be recruited during routine clinical exams at the Illinois Eye and Ear Infirmary.
 - .2 Available baseline corneal topography and pachymetry.
 - .3 Willingness to return for 4 study visits.
- Informed consent will be obtained by the principal investigator or co-investigators.

- Study visit number 1 (estimated 45-90 minutes)
 - .1 Patient demographics (age, race, age diagnosed with keratoconus) [standard of care]
 - .2 Past ocular and medical history including ocular procedures such as corneal collagen crosslinking and corneal surgery. [standard of care]
 - .3 Best corrected visual acuity with manifest refraction [standard of care]
 - .4 Corneal curvature using topography [standard of care]
 - .5 Corneal pachymetry (thickness) [standard of care]
 - .6 Meibography [standard of care] if already performed and present in the patient's medical record, the data will be gathered. However, it will not be completed solely for the purpose of this study. .

 - .7 Dry eye symptoms and contact lens comfort assessed using the validated 12-item OSDI and CLDEQ questionnaire. [for research purposes]
 - .8 Research intervention: Fitting for keratoconus [standard of care]
 - .8.1 Both eyes will be fit according to standard practices with the RoseK 2 corneal gas permeable and Synergeyes VS scleral lenses following manufacturer's recommendations.

.8.1.1 Over refraction and best corrected visual acuity.

.8.1.2 Subjective comfort with lens use rated on comfort scale of 0 (not comfortable) to 10 (very comfortable).

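### Section 9 defines the comfort comparison as OSDI and CLDEQ, while Section 3 makes a 0-10 rating the comfort outcome and gives OSDI and CLDEQ to dry-eye symptoms

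*Protocol*

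**What the plan says.** **Section 3.0 (Objectives/Aims).** The comfort hypothesis is "Scleral lens comfort will be rated higher than corneal gas permeable lenses". Secondary outcome 4 is "Subjective comfort with lens use rated on comfort scale of 0 (not comfortable) to 10 (very comfortable"). Secondary outcome 5 is a separate entry: "Dry eye symptoms assessed using the validated OSDI and CLDEQ". The Methods keep the two apart. At the fourth visit, "visual acuity, ease of use and subjective comfort of lens #2 will be assessed. The OSDI and CLDEQ questionnaires will be repeated"; the third visit is described in the same way for the first lens.

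**Section 9.0 (Data Analysis).** "Descriptive statistics will be used to compare logMAR visual acuity, comfort (OSDI and CLDEQ"), together with the number of lenses ordered, for lens #1 and lens #2. The 0-10 rating is not named. Section 12.0 adds only that the study is a pilot and the statistics are descriptive.

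**Section 6.0 (Study Design and Procedures).** Visit 1 has "Dry eye symptoms and contact lens comfort assessed using the validated 12-item OSDI and CLDEQ questionnaire". Visits 3 and 4 give OSDI to dry eye and CLDEQ to lens comfort, with the 0-10 rating as its own item. The survey paragraph says that OSDI, CLDEQ-8 and a comfort scale all assess dry-eye symptoms.

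**Remote contact.** Section 3.0 says "Participants unable to return for a study visit will be contacted to complete the surveys and final lens preference". The itemised list in Section 6.0 has the two questionnaires and the two lens-choice questions.

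**The concern.** The word *comfort* refers to one instrument in the outcome list and to two others in the analysis section. This is a conflict between two statements on the page, not a detail left for a statistical analysis plan. A plan's author could not tell from the protocol which measure answers the comfort hypothesis.

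The measures cannot stand in for one another:

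- **Direction.** A higher 0-10 rating is better. A higher OSDI score is worse (Section 6.0), and so is a higher CLDEQ-8 score by its printed response options.
- **Content.** Both questionnaires include vision items, and OSDI also asks about limits on activities. Section 3.0 treats acuity and comfort as separate outcomes, but under Section 9 a difference in vision between lenses could be reported as a difference in comfort.

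The 0-10 rating is taken at all four study visits, yet no analysis statement in the protocol uses it. This matters for the pilot's purpose: "This is a pilot study to determine sample size and feasibility of study protocol for a larger randomized study". The comfort measure carried into that planning should be unambiguous.

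**Working it through.** The protocol gives no figure to reproduce. The check compares the sections and then counts items on the forms in Appendix B.

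**1. Role of each instrument**

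| Place | 0-10 rating | OSDI | CLDEQ |
|---|---|---|---|
| Section 3.0, secondary outcomes | Comfort | Dry eye | Dry eye |
| Section 6.0, visit 1 | Separate item | Dry eye and comfort | Dry eye and comfort |
| Section 6.0, visits 3 and 4 | Separate item | Dry eye | Comfort |
| Section 6.0, survey paragraph | Dry eye (if this is the comfort scale named there) | Dry eye | Dry eye |
| Section 9.0 | Not named | Comfort | Comfort |

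Section 9 contradicts Section 3 for both questionnaires. Section 6 agrees with Section 9 on both only at visit 1; at visits 3 and 4, where the after-wear data arise, it agrees for CLDEQ but not for OSDI.

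**2. OSDI content**

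- Maximum raw score: 12 items × 4 = 48, taken as scaled linearly to the stated 0-100 range with all 12 items answered.
- Items 4-9 are blurred vision, poor vision, reading, night driving, computer or ATM use, and television: 6 of 12 items.
- One category better on those six, nothing else changed: 6/48 × 100 = **12.5 points**.
- Narrower reading, items 4 and 5 only (the two that name vision): 2/48 × 100 = **4.2 points**.

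**3. CLDEQ-8 content**

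- Item maxima as printed: 4 + 5 + 4 + 5 + 4 + 5 + 4 + 6 = 37.
- Blurry-vision items (3a, 3b): 4 + 5 = 9, and 9/37 = **24.3%** of the maximum.
- The last item is printed from 1 to 6, so the attainable range is 1 to 37, a span of 36. On that base the share is 9/36 = 25.0%.
- One category on both blur items is 2 points: 2/37 = 5.4%, or 2/36 = 5.6% of the span.

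**4. After-wear comfort ratings per participant**

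- Visit 3 item .3 (first lens) and visit 4 item .3 (second lens): 2 ratings, one pair.
- The remote-contact list repeats visit 4 items .4 to .6 but not .3. Read literally, a participant completed remotely in place of visit 4 has 2 − 1 = 1 after-wear rating and no pair. The only rating of the second lens is then the one taken on the day it was dispensed (visit 3 item .7).

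**The case against.** The strongest reply is that Section 9 has support elsewhere and that little depends on the label. Visit 1 in Section 6 does link both questionnaires to lens comfort, visits 3 and 4 give CLDEQ to comfort, and the first CLDEQ-8 question is about eye discomfort. Each instrument has its own line on the data collection form, no composite is planned, and Section 9 names its instruments in brackets, so the data could be separated later. Comfort is secondary, and the primary outcome, final lens choice, is untouched. All of this is true and limits the seriousness. It does not remove the conflict: Section 6 gives three assignments, and two of them disagree with Section 9 on OSDI.

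The 12.5-point figure can also be challenged. OSDI items 6-9 ask about activity limits, which discomfort can cause as well as poor vision. That is fair: the figure covers vision and activity items together, and the vision-only figure is 4.2 points. Neither predicts a result.

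On remote contact, *the surveys* may be meant to include the 0-10 rating, especially if the comfort scale in the survey paragraph is that rating. If it is a different scale, the third labelling in Section 6 loses force for the rating, though not for CLDEQ. The remote-contact gap is therefore possible, not certain, and the main point does not depend on it.

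Finally, time points and a paired summary are ordinary content of an analysis plan. Their absence is not the criticism; the criticism is that Section 9 attaches comfort to the wrong instruments.

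**Conclusion.** The concern holds. Section 3 makes the 0-10 rating the comfort outcome and gives OSDI and CLDEQ to dry eye; Section 9 states the comfort comparison on OSDI and CLDEQ; Section 6 supports more than one reading. As written, the comfort hypothesis would be judged on questionnaires that run the other way from the rating and partly measure vision and activity limits. The size is illustrated by 12.5 OSDI points for one category on items 4-9 (4.2 on items 4-5 alone) and by a blur share of about a quarter of the CLDEQ-8. These figures rest on the printed forms, linear OSDI scaling and complete answers.

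No power, error rate or sample size is affected, and neither the number of remote contacts nor the size of any bias can be derived from the protocol. The text should be corrected, but the defect does not undermine the trial.

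**What to change.** - **Section 9.0:** name the 0-10 rating after 2-4 weeks of wear (visits 3 and 4) as the comfort outcome. Compare it within participant by lens type, scleral against corneal, and report the standard deviation, which serves the aim of determining sample size. Use lens type rather than number, because lens #1 is the scleral product in the product list but the first-dispensed lens in the visit schedule.
- **Section 9.0:** report OSDI and CLDEQ-8 separately as dry-eye and lens-symptom outcomes, stating that higher is worse for both.
- **Section 6.0:** use the same labels at visit 1, at visits 3 and 4, and in the survey paragraph.
- **Section 6.0, remote contact:** add the 0-10 rating of the second lens to the list, or state that the surveys include it.

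The cost is wording in two sections, at most one extra question at remote contact, and a simple paired summary. No participants or visits are added, and the study remains a descriptive pilot.

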10.0 Quality Control and Quality Assurance

- The principal investigator will provide training for all co-investigators on recruitment, obtaining informed consent and proper filling out of case report forms.
- The principal investigator will review de-identified data entered into RedCAP after every 5 participants for completeness. REDCap limits will be used to ensure responses fall within appropriate ranges.

- The principal investigator will review de-identified data from each study sites to ensure data completeness and accuracy.

11.0 Data and Safety Monitoring

- There will not be a data and safety monitoring committee for this study. All study related problems will be identified and reported to the principal investigator. All co-investigators will be responsible for reporting safety concerns to the PI within 48 hours of occurrence.
- Adverse Events (AEs) will be collected and reviewed by the principal investigator within one business day.
- Unanticipated problems (UPs) will be detailed by co-investigators and reported to the principal investigator within one business day. Any study related AEs or UPs outside of usual contact lens related or contact lens handling problems will be reported to the IRB.
- A participant may elect to withdraw or stop participating in the study at any time.

12.0 Statistical Considerations

- This is a pilot study to determine feasibility for a future randomized clinical trial. Descriptive statistics will be compiled.

13.0 Regulatory Requirements

13.1 Informed Consent

- Informed consent will be obtained by the investigators at each site during routine ophthalmology or optometry visits.
- The principal investigator will train the co-investigators to use a script to obtain informed consent.
- Paper copies of informed consent documents will be provided to the study participant and maintained by the principal investigator in a locked file cabinet of locked office.
- No minors will be enrolled in this study.
- In person translators will be used to enroll non-English speaking participants if applicable. If in person translators are unavailable, the study visit can be rescheduled until an in person translator is available.

13.2 Subject Confidentiality

- Study participants will be recruited and complete informed consent in a clinical exam lane with a closed door by the principal investigator or co-investigator.
- Only the principal and co-investigators will have access to the study data for each participant at their individual site.

- Study data will be de-identified and entered into the REDCap database.
- After completion of the study, the master list linking participants to their study will be destroyed.
- De-identified data only will be maintained in RedCAP for analysis and publication.
- PHI will be viewed during routine clinical visits while viewing the electronic medical record.


APPENDICES

A. Eligibility Checklist

- Diagnosis of keratoconus confirmed by slit lamp and topography.
- No history of corneal surgery or INTACS (history of CXL okay)
- No prior history of prior hybrid, corneal or scleral gas permeable lens use.
- Age 18 or older
- Willing to return for 4 study visits.

Recruitment script:

“You may qualify to participate in a research study for patients with keratoconus with corrective contact lenses. As part of the study, participants are fit with two types of contact lenses and asked questions about their experience with each lens type. If you are interested in hearing more about the study I can provide more information and a copy of the written informed consent which outlines more details of the study. If you are not interested in participating in the study there will be no negative impact on your ongoing care.

B. Data Collection Forms

Study ID #

Date of signed informed consent

Randomization lens #1 →#2 or lens #2 →#1

*Odd # study id will begin with lens #1.

- Study visit number 1
 - .1 Patient demographics
 - .1.1 Age
 - .1.2 Race
 - .1.3 Age diagnosed with keratoconus
 - .2 Past ocular and medical history including ocular procedures such as corneal collagen crosslinking and corneal surgery.
 - .3 Best corrected visual acuity with manifest refraction
 - .4 Corneal curvature using topography
 - .5 Corneal pachymetry (thickness)
 - .6 Meibography

Initial correction keratoconus: corneal gas permeable vs scleral lens

- .7 *OSDI questionnaire*
- .8 *CLDEQ questionnaire*
- .9 *Lens fitting data*
 - .9.1 *Trial lens*
 - .9.2 *CL fitting evaluation*
 - .9.3 *Over refraction and best corrected visual acuity.*
 - .9.4 *Subjective comfort with lens use rated on comfort scale of 0 (not comfortable) to 10 (very comfortable)*
- *Study visit number 2*
 - .1 *Randomization: lens type corneal gas permeable or scleral lens*
 - .2 *Time started/finished lens application and removal handling*
 - .3 *Best corrected visual acuity with lens #1*
 - .4 *Subjective comfort with lens use rated on comfort scale of 0 (not comfortable) to 10 (very comfortable)*
- *Study visit number 3*
 - .1 *Best corrected visual acuity with lens #1*
 - .2 *Hours of lens wear today, average hours of lens wear time, days per week of per week and daily time spent on lens application and removal*
 - .3 *Subjective comfort with lens use rated on comfort scale of 0 (not comfortable) to 10 (very comfortable)*
 - .4 *OSDI questionnaire*
 - .5 *CLDEQ questionnaire*
 - .6 *Time started/finished application and removal handling*
 - .7 *Best corrected visual acuity with lens #2*
 - .8 *Subjective comfort with lens use rated on comfort scale of 0 (not comfortable) to 10 (very comfortable)*
- *Study visit number 4*
 - .1 *Best corrected visual acuity with lens #2*
 - .2 *Hours of lens wear today, average hours of lens wear time, days per week of per week and daily time spent on lens application and removal*
 - .3 *Subjective comfort with lens use rated on comfort scale of 0 (not comfortable) to 10 (very comfortable)*
 - .4 *OSDI questionnaire*
 - .5 *CLDEQ questionnaire*
 - .6 *Participant final selection of lens of choice #1 or #2*
 - .7 *Participant final selection of lens of choice #1 or #2 given average self-pay cost of annual replacement.*

Non-study visits

Lens #1- number of lenses needed to finalize

Lens #2- number of lenses needed to finalize

Unscheduled visits

.1 Study ID

Date

Reason for unscheduled visit

Lens type unscheduled visit is related to (corneal gas permeable or scleral lens)

Lens loss

Lens breakage

Other problem (describe)

Len cessation advised? Yes/No

Adverse Event reporting

Study ID

Date

Type of adverse event:

Medical treatment required:

Len cessation advised? Yes/No

Questionnaires

OSDI 12

CLDEQ-8

Initial correction keratoconus: corneal gas permeable vs scleral lens

Ocular Surface Disease Index[®] (OSDI[®])²

Ask your patients the following 12 questions, and circle the number in the box that best represents each answer. Then, fill in boxes A, B, C, D, and E according to the instructions beside each.

Have you experienced any of the following during the last week ?	All of the time	Most of the time	Half of the time	Some of the time	None of the time
1. Eyes that are sensitive to light? . .	4	3	2	1	0
2. Eyes that feel gritty?	4	3	2	1	0
3. Painful or sore eyes?	4	3	2	1	0
4. Blurred vision?	4	3	2	1	0
5. Poor vision?	4	3	2	1	0

Subtotal score for answers 1 to 5

Have problems with your eyes limited you in performing any of the following during the last week ?	All of the time	Most of the time	Half of the time	Some of the time	None of the time	N/A
6. Reading?	4	3	2	1	0	N/A
7. Driving at night?	4	3	2	1	0	N/A
8. Working with a computer or bank machine (ATM)?	4	3	2	1	0	N/A
9. Watching TV?	4	3	2	1	0	N/A

Subtotal score for answers 6 to 9

Have your eyes felt uncomfortable in any of the following situations during the last week ?	All of the time	Most of the time	Half of the time	Some of the time	None of the time	N/A
10. Windy conditions?	4	3	2	1	0	N/A
11. Places or areas with low humidity (very dry)?	4	3	2	1	0	N/A
12. Areas that are air conditioned? . . .	4	3	2	1	0	N/A

Subtotal score for answers 10 to 12

Add subtotals A, B, and C to obtain D
(D = sum of scores for all questions answered)

Total number of questions answered
(do not include questions answered N/A)

Please turn over the questionnaire to calculate the patient's final OSDI[®] score.

Patient/Subject #: _____ Date: ___/___/___ Time: _____

**CONTACT LENS QUESTIONNAIRE-8
(CLDEQ-8)**

1. Questions about EYE DISCOMFORT:

a. During a typical day in the past 2 weeks, **how often** did your eyes feel discomfort while wearing your contact lenses?

- 0 Never
- 1 Rarely
- 2 Sometimes
- 3 Frequently
- 4 Constantly

When your eyes felt discomfort with your contact lenses, **how intense** was this feeling of discomfort...

b. At the end of your wearing time?

Never have it	Not at All Intense				Very Intense
0	1	2	3	4	5

2. Questions about EYE DRYNESS:

a. During a typical day in the past 2 weeks, **how often** did your eyes feel dry?

- 0 Never
- 1 Rarely
- 2 Sometimes
- 3 Frequently
- 4 Constantly

When your eyes felt dry, **how intense** was this feeling of dryness...

b. At the end of your wearing time?

Never have it	Not at All Intense				Very Intense
0	1	2	3	4	5

3. Questions about CHANGEABLE, BLURRY VISION:

a. During a typical day in the past 2 weeks, **how often** did your vision change between clear and blurry or foggy while wearing your contact lenses?

- 0 Never
- 1 Rarely
- 2 Sometimes
- 3 Frequently
- 4 Constantly

When your vision was blurry, **how noticeable** was the changeable, blurry, or foggy vision ...

b. At the end of your wearing time?

Never have it	Not at All Intense				Very Intense
0	1	2	3	4	5

4. Question about CLOSING YOUR EYES:

During a typical day in the past 2 weeks, **how often** did your eyes bother you so much that you wanted to close them?

- 0 Never
- 1 Rarely
- 2 Sometimes
- 3 Frequently
- 4 Constantly

5. Question about REMOVING YOUR LENSES:

How often during the past 2 weeks, did your eyes *bother you so much* while wearing your contact lenses that you felt as if you needed to stop whatever you were doing and **take out your contact lenses**?

- 1 Never
- 2 Less than once a week
- 3 Weekly
- 4 Several times a week
- 5 Daily
- 6 Several times a day

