1.0 Project Summary/Abstract

- This is a multi-center, randomized interventional clinical trial with a 2x2 crossover design of patients with keratoconus fit with corneal and scleral gas permeable contact lenses.
- While both corneal gas permeable and scleral lenses have been shown to improve visual acuity in individuals with keratoconus, it has yet to be determined if one option has superior comfort and overall patient satisfaction in patients new to gas permeable lens use.

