5.0 Subject Enrollment

- After identification, potential participants will be asked if they would like to hear more about the study during routine clinical visits.
- A standardized recruitment script will be used by study investigators.
- The informed consent document will be reviewed with potential participants.
- Individuals with a diagnosis of keratoconus meeting all inclusion and exclusion criteria and willing to participate will be enrolled by the principle and co-investigators.
- Participants will be compensated \$40 (Visa gift cards) for each of the four study visits at the completion of the study. The patient will receive their final selected lens of choice at no cost.

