- Routine Follow up visits to evaluate lens fit and visual acuity according to standard practice until lenses are deemed adequate for dispensing. [standard of care].
- Study visit number 2 (estimated 30-60 minutes)
 - .1 Randomize to dispense lens #1 vs lens #2. [for research purposes]
 - .2 Lens application and removal handling [standard of care].
 - .3 Instructions on lens disinfection procedures.
 - .4 Best corrected visual acuity with lens #1 [standard of care]
 - .5 Subjective comfort with lens use rated on comfort scale of 0 (not comfortable) to 10 (very comfortable) [for research purposes].
- Study visit number 3- wearing lens #1 between 2-4 weeks for minimum of 3 hours (estimated 45-75 minutes)
 - .1 Best corrected visual acuity with lens #1 [standard of care]
 - .2 Hours of lens wear today, average hours of lens wear time, days per week of per week and daily time spent on lens application and removal (general question – patients will not need to keep track or a log) [standard of care]
 - .3 Subjective comfort with lens use rated on comfort scale of 0 (not comfortable) to 10 (very comfortable) [for research purposes].
 - .4 Dry eye symptoms assessed (OSDI questionnaire), contact lens comfort assessed (CLDEQ). [for research purposes]
 - .5 Lens #2 application and removal training [for research purposes].
 - .6 Best corrected visual acuity with lens #2 [standard of care].
 - .7 Subjective comfort with lens use rated on comfort scale of 0 (not comfortable) to 10 (very comfortable) [for research purposes].
- Study visit number 4- wearing lens #2 between 2-4 weeks for minimum of 3 hours (estimated 15-45 minutes)
 - .1 Best corrected visual acuity with lens #2 [standard of care]
 - .2 Hours of lens wear today, average hours of lens wear time, days per week of per week and daily time spent on lens application and removal (general question – patients will not need to keep track or a log) [standard of care]
 - .3 Subjective comfort with lens use rated on comfort scale of 0 (not comfortable) to 10 (very comfortable) [for research purposes].
 - .4 Dry eye symptoms assessed (OSDI questionnaire), contact lens comfort assessed (CLDEQ). [for research purposes]

- .5 Participant final selection of lens of choice #1 or #2 [for research purposes].
- .6 Participant final selection of lens of choice #1 or #2 given average self-pay cost of annual replacement [for research purposes].

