- Final participant preferences- participants can be contacted to complete the surveys and final lens preference,
 - .1 Dry eye symptoms assessed (OSDI questionnaire), contact lens comfort assessed (CLDEQ). [for research purposes]
 - .2 Participant final selection of lens of choice #1 or #2 [for research purposes].
 - .3 Participant final selection of lens of choice #1 or #2 given average self-pay cost of annual replacement [for research purposes].
- Unscheduled visits
 - Will tally unscheduled visits and current lens type. [standard of care]

For Studies that Collect Prospective Data

- Data will be collected prospectively from the electronic medical record using paper care report forms and RedCAP by the primary and co-investigators at all study sites.
- A master list will be used to code participants and maintain study documents with study ID only. The list will be maintained by the investigator at each study site. De-identified data only will be shared with co-investigators listed on the study and with the locations listed on this study. The list will be stored in a locked cabinet of a locked office.
- At the completion of the study, the lists will be destroyed.
- De-identified data only will be maintained for future research use.

Survey studies

- Participants will complete the validated 12-item OSDI¹⁰ and the Contact lens dry eye questionnaire-8 (CLDEQ-8)¹¹ and comfort scale of contact lens performance to assess dry eye symptoms at each study visit.
- The OSDI Score is assessed on a scale of 0 to 100 with higher scores representing greater disability.

Studies involving use of product

- Two products will be used in this study.
 - Contact lens #1: SynergEyes VS (Synergeyes, Inc., Carlsbad CA) which features bi-tangential toric peripheries with linear landing zones. The standard lens is 16.0mm and is available from 14.5 to 17.5mm diameters.
 - Contact lens #2: RoseK2 corneal gas permeable lens (Blanchard Contact Lens, Inc. Manchester, NH). The lens is available in with a base

Initial correction keratoconus: corneal gas permeable vs scleral lens

curve range from 4.30 to 8.60 mm, diameter of 7.90 to 10.40mm.

- Product information including lens order number, lens parameters, lens materials and verification will be tracked and maintained in the case report form and on RedCAP.
- Adverse events will be recorded and immediately reported to the clinic PI.

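### The protocol calls the trial randomized with allocation at visit 2, but its only allocation rule is study-ID parity, so lens order is fixed and unconcealed once the ID is known

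*Protocol*

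**What the plan says.** Section 1.0 states: "This is a multi-center, randomized interventional clinical trial with a 2x2 crossover design". Section 6.0 repeats the label and refers to two randomized groups. The Methods in section 3.0 fix the time of allocation: "At the 2nd study visit, patients will be randomized to receive lens application and removal training with lens type #1". The visit 2 procedures in section 6.0 agree: "Randomize to dispense lens #1 vs lens #2". By then both lens types have been fitted in both eyes, with follow-up visits "until lenses are deemed adequate for dispensing".

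None of these sections says how the order is generated. The one rule is in Appendix B, beside the study ID, consent date and randomization lines that head the form above the visit 1 items: "Odd # study id will begin with lens #1". The rule for even IDs is implied. The product description in section 6.0 identifies the lens: "Contact lens #1: SynergEyes VS", which is the scleral lens. Lens #2 there is the corneal gas permeable lens.

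Under section 5.0, participants "will be enrolled by the principle and co-investigators". Under section 6.0 the investigators also collect the data, and each site's investigator keeps the list linking participants to study IDs. REDCap is named for data entry, range limits and storage, but not for allocation.

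**The concern.** A parity rule is deterministic given the ID, so the design described in the body of the protocol is not the one the form carries out. Parity fixes which lens is worn first, not which lenses are received. Order still matters in three places.

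- **By-sequence display.** Section 9.0 tabulates final lens selection by randomization group. The comparison between groups is fair only if sequence is unrelated to patient type.
- **Who reaches the final choice.** Under section 3.0, a participant who refuses to give back the first lens leaves the study before the visit 4 choice. Order can therefore influence who is counted, and only sound allocation ensures that the two groups exposed to this were comparable at the start.
- **Readiness for dispensing.** This is a clinician's judgement made before visit 2, probably with the order already readable.

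The study is also a pilot meant to test the feasibility of a protocol for a larger randomized trial. Under a parity rule, concealed allocation goes untested.

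**Working it through.** **1. The passages side by side.** Sections 1.0, 3.0 and 6.0 say randomized, and sections 3.0 and 6.0 place the act at visit 2. Appendix B says parity of the study ID. No section mentions a random sequence, generator, blocking, stratification, envelopes or central allocation. The form also has a randomization entry under visit 2, consistent with sections 3.0 and 6.0, but parity has already settled what is written there.

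**2. Meaning of lens #1.** The visit schedule also uses lens #1 for whichever lens is worn first. On that reading the parity note is empty, since everyone begins with the first lens worn. Only the product numbering gives it content: odd means scleral first.

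**3. Enrolment and balance.** Section 6.0 gives 25 per clinic and a maximum of 125; 5 × 25 = 125 reproduces. If IDs run consecutively from 1 (assumed), a full site has 13 odd and 12 even. One common series gives 63:62; a separate series per site gives 5 × 13 = 65 against 5 × 12 = 60.

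**4. Predictability.** Under parity, someone who knows the IDs names the order correctly for 25 of 25 at a full site. Under simple 1:1 randomization the expected number is 12.5 of 25, and the chance of 18 or more is about 0.022.

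**5. Pooled scleral share.** Let an order effect of e points raise the scleral share by e in one sequence and lower it by e in the other (a gap of 2e). With 65:60 the pooled shift is e × (65 − 60)/125 = 0.04e:

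| Assumed e (points) | Pooled shift (points) |
|---|---|
| ±5 | 0.2 |
| ±10 | 0.4 |
| ±20 | 0.8 |

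If the effect is instead defined as the whole gap, these shifts halve.

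Now suppose 25 of 125 are lost independently of sequence (assumed). The SD of the odd count among the remaining 100 is √(100 × 0.52 × 0.48 × 25/124) = 2.24. The range 52 ± 1.96 × 2.24 is 47.6 to 56.4, so the odd share f lies in about 48% to 56%. With e = 10, the shift 10 × (2f − 1) runs from −0.5 to +1.3 points.

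**6. Between-sequence gap.** This needs consecutive IDs and selective enrolment, neither of which is stated. Take 62 per sequence and exchange one pair whose probabilities of choosing the scleral lens differ by d. One group's share rises by d/62 and the other's falls by d/62, so the gap moves by 2d/62 and the pooled share not at all.

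- d = 0.3: 0.6/62 = 1.0 point
- d = 0.6: 1.2/62 = 1.9 points

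At an assumed 60% share, the standard error of the gap is √(2 × 0.6 × 0.4/62) = 8.8 points. Then 8.8/1.94 = 4.5 and 8.8/0.97 = 9.1, or about 5 to 9 exchanges for one standard error.

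**The case against.** The strongest reply is that this is a descriptive pilot in which everyone is meant to wear both lenses. The hypothesis concerns overall preference, and the overall share hardly moves. That stands, and it caps the severity.

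Several narrower points also stand:

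- A 65:60 split is no worse than chance. Simple randomization of 125 gives an expected absolute difference of √(2 × 125/π) ≈ 8.9, against 5 here. The defect is predictability, not imbalance.
- Losing participants who keep the first lens would happen under true randomization too, and changing the allocation method does not remove it.
- The position of a line on a form does not prove when an ID is issued or a field filled in. That the order is readable during fitting is likely, not established, and no direction of bias in the readiness judgement can be named.
- Knowing the next participant's order before consent requires consecutive IDs and, in practice, a series the site can follow. Neither is stated.
- The exchange figures require investigators to guess the eventual preference of patients who have never worn hybrid, corneal or scleral gas permeable lenses. The standard error is only a yardstick, since the protocol plans no test of the gap.

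None of this touches the core. The method has not been left to another document: the protocol states one, on the form that sites use. Even if IDs were issued at random, the order would still be readable from the ID.

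**Conclusion.** The concern holds. The stated design is randomized with allocation at visit 2; the stated rule is parity, which is quasi-random and unconcealed once the ID is known. That contradiction rests on the text alone and is held with high confidence.

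Its numerical consequence is modest. The pooled scleral share shifts by 0.2 to 0.8 points under the assumed order effects and a 65:60 split, and counts by lens type during fitting are affected little while the sequences stay near balance. The display by randomization group is more vulnerable, but the figures of 1.0 to 1.9 points per exchanged pair rest on assumed consecutive IDs, selective exchange and assumed differences in preference. They show what the rule permits, not bias that has been demonstrated. The point should be fixed because the randomized label is not supported as written and the remedy is cheap.

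**What to change.** Delete the odd-ID note from Appendix B. Replace it with a computer-generated random sequence unrelated to study ID, for example blocked by site with varied block sizes. Hold it centrally, or in REDCap if its randomization function is available to the study (an assumption; the protocol does not say). Release each assignment only at visit 2, after both lens types have been recorded as adequate for dispensing, and keep the visit 2 entry as the only randomization field. Name the sequences scleral-first and corneal-first, so that lens #1 no longer means both a product and the first lens worn.

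For participants already allocated by parity, describe the method as quasi-random in any report.

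The cost is a short amendment and the setting up of the list, with no added patients or visits.
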